16.2 Best Corrected Visual Acuity

Best Corrected Visual Acuity will be taken at all visits during the observational period. Best correct visual acuity collected during the observation period will be summarized similarly to that of treatment period.

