In subjects who develop cornea verticillata, CS and BCVA will be summarized at the eye level (that is, if a subject has a cornea verticillata in both eyes, then both eyes will be included) for the initial assessments and for follow-up visits as well as change from the initial assessment (for visual acuity, change from baseline, as defined for the Treatment Period will also be completed), by treatment group and by whether or not the cornea verticillata deposit event is ongoing at given visit. The VFQ-25 scores will be summarized similarly at the subject level.

Resolution of cornea verticillata is defined as a cornea verticillata deposit grade of zero. Stabilization is defined as no worsening of the cornea verticillata grading for a minimum of one year from the commencement of dosing. The time to cornea verticillata resolution/stabilization will be evaluated in days related to start date of cornea verticillata at the eye level. Kaplan-Meier methods will be used to estimate median time to cornea verticillata resolution/stabilization, as well as the 25th and 75th percentiles by treatment group and overall netarsudil treated subjects. Associated 95% confidence interval will also be estimated. Kaplan-Meier curves will also be presented by treatment group and overall netarsudil treated subjects.

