7.4 Cornea Verticillata Safety Population

The cornea verticillata safety population will include all subjects in the safety population who develop cornea verticillata during the study. This population will be used to summarize safety variables within the observational period and will summarize subjects as treated.

8. General Statistical Considerations

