15.2 Best Corrected Visual Acuity

Best corrected visual acuity will be measured using Landolt-C chart or its equivalents at Visit 1, Visit 2, Visit 3.0, Visit 4.0, Visit 5.0, and Visit 6.0.

Best corrected visual acuity data for both the study eye and the fellow eye will be summarized for each visit and for change from baseline to each post-treatment visit using the continuous summary statistics.

A subject listing of the BCVA results will be produced.

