16.1 Visual Function Questionnaire

The subjects who develop cornea verticillata will undergo VFQ-25 at OBS Visit 1 (when cornea verticillata is diagnosed) and the final visit. The scores and the score changes from OBS Visit 1 will be summarized using the continuous summary statistics by treatment group.

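### SAP 16.1 and 16.2 drop the ongoing-versus-resolved split for VFQ-25 and BCVA in the observational period, and 16.2 does not limit the BCVA tables to affected eyes

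*SAP*

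**What the plan says.** Protocol 9.7.2 (Observational Period) plans contrast sensitivity (CS) and BCVA at the level of the eye and explains what that means: "if a subject has a cornea verticillata in both eyes, then both eyes will be included". Results are to be shown "by treatment group and by whether or not the cornea verticillata deposit event is ongoing at given visit". For the questionnaire it adds: "The VFQ-25 scores will be summarized similarly at the subject level".

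The SAP treats the four measures differently:

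- **BCVA, SAP 16.2:** "Best correct visual acuity collected during the observation period will be summarized similarly to that of treatment period". The treatment-period rule it points to, SAP 15.2, reads: "Best corrected visual acuity data for both the study eye and the fellow eye will be summarized for each visit". Neither section mentions deposit status or affected eyes.
- **VFQ-25, SAP 16.1:** "The scores and the score changes from OBS Visit 1 will be summarized using the continuous summary statistics by treatment group". No split by deposit status.
- **CS and grading, SAP 16.3 and 16.4:** by eye, with the split by ongoing event kept (in 16.3 it is stated for the discrete summary).

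The analysis population (SAP 7.4) is defined by subject: it "will include all subjects in the safety population who develop cornea verticillata during the study". The SAP table list titles the BCVA, CS and grading tables (14.4.5.1 to 14.4.7.2) by study eye or fellow eye. No title from 14.4.4 to 14.4.7.2 names a split by deposit status.

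**The concern.** Protocol 3.2 gives the reason for the observational period: to learn how verticillata affects visual function and how it resolves in Japanese subjects, after discussion with the regulator. That requires comparing function while a deposit is present with function after it has cleared. BCVA is the only visual-function measure planned at every observational visit; VFQ-25 and CS are planned at OBS Visit 1 and the Final Visit only. BCVA and VFQ-25 are the two measures for which the SAP text leaves out the comparison.

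The unit also matters. If a subject has a deposit in one eye only, the study-eye and fellow-eye layout gives the unaffected eye a place in one of the two BCVA tables, because nothing excludes it.

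**Working it through.** No figure in the plan is in dispute. The check is a comparison of text, followed by a sketch of what the omissions could do.

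**Step 1. The rules side by side.**

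| Measure | Protocol 9.7.2 | SAP text | SAP table titles |
|---|---|---|---|
| BCVA | by eye, affected eyes; ongoing split | 16.2, via 15.2: study and fellow eye by visit; no split | 14.4.5.1-2: study/fellow eye; no split |
| VFQ-25 | by subject; same split | 16.1: by treatment group; no split | 14.4.4: no split |
| CS | by eye, affected eyes; ongoing split | 16.3: by eye; split kept | 14.4.6.1-2: study/fellow eye; no split |
| Grading | none in 9.7.2 (synopsis: by eye, similar manner) | 16.4: by eye; split kept | 14.4.7.1-2: study/fellow eye; no split |
| Time to resolution/stabilization | by eye, from onset | 16.5: same | 14.4.7.3-4 |

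That only affected eyes count is the natural reading of the protocol's parenthesis on bilateral cases. The SAP states no such limit in 16.2, 16.3 or 16.4.

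**Step 2. Where the missing split matters.**

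- OBS Visit 1: every subject has a deposit, so nothing is mixed at subject level.
- Interim visits: a subject returns while a deposit persists and exits only when both eyes have resolved or stabilized. BCVA is mixed when one eye clears before the other.
- Final Visit: a subject may exit with grade zero or as stabilized. Stabilized means no worsening for at least one year from the start of dosing, so the deposit can still be there. BCVA and VFQ-25 are both mixed here, whether or not any case is unilateral.

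**Step 3. Direction at the Final Visit.** Assume a deficit D while a deposit is present and none once it clears. Let s be the share of stabilized cases at the Final Visit. Neither D nor s is in the documents.

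- Pooled residual deficit = s·D + (1 − s)·0 = s·D. The value in persisting cases is D.
- Pooled recovery since OBS Visit 1 = D − s·D = (1 − s)·D. The value in cleared cases is D.

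With s = 0.25 the table shows a deficit of 0.25·D and a recovery of 0.75·D. With s = 0.50 it shows 0.50·D for each. Pooling understates the deficit under persisting deposits and also the recovery after clearing.

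**Step 4. Never-affected eyes in the BCVA tables.** Let u be the share of unilateral cases, with the affected eye equally likely to be study or fellow eye. The share of affected eyes in each table, and so the fraction of a true mean effect that is kept, is 1 − u/2.

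| u (assumed) | 1 − u/2 | Dilution |
|---|---|---|
| 0 | 1.00 | 0% |
| 0.10 | 0.95 | 5% |
| 0.25 | 0.875 | 12.5% |
| 0.50 | 0.75 | 25% |
| 1 | 0.50 | 50% |

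If a share r of affected eyes has cleared and cleared eyes have no deficit, an unsplit mean keeps (1 − u/2)(1 − r). With r = 0.5 this is 0.50 at u = 0, 0.44 at u = 0.25 and 0.375 at u = 0.50.

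**Step 5. CS and grading.** The split keeps a never-affected eye out of the ongoing stratum, so the factor in Step 4 does not apply there. Such an eye could still fall in the other stratum beside resolved eyes. Its share there is (u/2) / [u/2 + (1 − u/2)·r]. For u = 0.25 this is 0.36 (r = 0.25) or 0.22 (r = 0.5). For u = 0.50 it is 0.57 or 0.40.

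**Step 6. How many cases.** Protocol 1.1 reports 76/454 = 16.7% of subjects on once-daily netarsudil. Applied to 52 per arm: 52 × 76/454 = 8.7. Over three active arms: 156 × 76/454 = 26. This is only a rough guide. Onset in those studies ran from 2 to 13 weeks while dosing here lasts 28 days, which points to fewer; the protocol also calls the finding dose dependent, and that rate need not fit every arm.

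**The case against.** A reader might infer more than the documents support, and several counterarguments stand:

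- **That all observational tables average unaffected with affected eyes.** They do not. CS and grading keep the eye level and the split in the text, and a short table title does not cancel it. Kaplan-Meier time runs from each eye's verticillata start date, so a never-affected eye has no time origin.
- **That the SAP invented a subject-based population.** Protocol 9.3.4 defines it in the same terms, and VFQ-25 by subject is the protocol's own rule.
- **That dilution is established.** It is an inference from silence in 16.2 and needs unilateral cases. All subjects dose both eyes, the unilateral share is not given, and it may be zero.
- **That the error always reassures.** Step 3 shows that recovery can be understated too.
- **That SAP 18 hides a departure.** The SAP implements protocol Amendment 2, and the protocol available is Amendment 1. Whether section 18 is incomplete cannot be tested.

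The consequence is also limited. These are descriptive summaries without hypothesis tests, and Listings 16.3.4 to 16.3.7 let a reader match function to deposit status case by case.

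The core survives. SAP 16.1 and 16.2 omit a split that 16.3 and 16.4 keep, an inconsistency within the SAP whichever amendment applies. The SAP states that its methods supersede the protocol's, so the protocol does not fill the gap. Mixing of resolved and stabilized cases at the Final Visit does not depend on u.

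**Conclusion.** The point holds in limited form. Against Protocol 9.7.2 (Amendment 1) and against its own sections 16.3 and 16.4, the SAP omits the ongoing split for VFQ-25 and BCVA, and 16.2 does not say that only affected eyes count. Followed as written:

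- Final Visit BCVA and VFQ-25 pool resolved with stabilized cases.
- Interim BCVA mixes eyes that have and have not cleared.
- In a unilateral case the unaffected eye can enter the BCVA tables, or the stratum without an ongoing event for CS and grading.

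The size and direction are unknown. Dilution from unaffected eyes runs from 0% (all bilateral) to at most 50% (all unilateral, evenly divided between study and fellow eyes), and the values of u, r and s used above are assumptions. Time to resolution is unaffected. Because the summaries are descriptive and cases are probably few, priority is low to moderate.

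**What to change.** 1. In SAP 16.1 and 16.2 (Tables 14.4.4 and 14.4.5.1-2), restore the split at each visit between ongoing and resolved. Apply it per eye for BCVA, and per subject for VFQ-25, counting a subject as ongoing if either eye still has a deposit. Stabilized cases with deposits then stay apart from resolved ones at the Final Visit.
2. In SAP 16.2 to 16.4, limit eye-level summaries to eyes with a recorded verticillata event. For BCVA and CS this follows Protocol 9.7.2. For grading, the protocol basis is the synopsis.
3. Show the split that 16.3 and 16.4 already require in Tables 14.4.6.1-2 and 14.4.7.1-2.
4. If the unsplit layout is intended, state it and give the reason, after checking it against Amendment 2.

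The cost is SAP and table-shell wording plus one eye-level flag derived from grading data already collected. No new data are needed.

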16.3 Contrast Sensitivity Testing

The CS testing will undergo at OBS Visit 1 (when cornea verticillata is diagnosed) and the final visit. The CS results will be summarized at eye level using discrete summary statistics for each spatial frequency by treatment group, and by whether or not the corneal verticillata deposit event is ongoing at given visit. The numeric part of the CS results will be summarized at eye level using the continuous summary statistics.

16.4 Cornea Verticillata Grading

Subjects who are diagnosed with cornea verticillata by slit lamp examination will undergo grading of the corneal deposits using a published grading scale for amiodarone-induced cornea verticillata. The corneal deposits will be graded at all visits during the observational period. The scores and the score changes from Visit 1 will be summarized at eye level using continuous summary statistics by treatment group, and by whether or not the cornea verticillata deposit event is ongoing at given visit.

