7.4 Observational Period

Subjects will undergo the following visits until resolution/stabilization of the cornea verticillata. Resolution of the cornea verticillata will occur when a subject has a cornea verticillata grading of zero in both eyes. Stabilization is defined as no worsening of the

cornea verticillata grading for a minimum of one year from the commencement of dosing. The duration of the observational period will vary from subject to subject.

7.4.1 OBS Visit 1 (any visit between Visits 4 to 6 when cornea verticillata is detected)

Subjects will discontinue study medication and undergo the following assessments:

- Completion of Visit 6 procedures (Exit Visit)
- Concomitant medication use
- VFQ-25
- BCVA
- CS testing
- Cornea verticillata grading

7.4.2 OBS Visits 2, 3 and 4 (3 monthly visits 1 month (30 ± 5 days) from prior OBS Visit)

At each monthly visit, the subject should be questioned regarding any changes in their health or concomitant medication use. The following procedures will be performed:

- BCVA
- Cornea verticillata grading

If cornea verticillata grading is higher than zero at this Month 1 Visit, the subject will return for a Second and/or Third Monthly Visit at which the procedures and assessments done at the first Monthly Visit will be repeated.

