7.4.4 Final Study Visit Procedures

Upon resolution or stabilization of cornea verticillata at any OBS Visit, subjects will be questioned regarding any changes in their health or concomitant medication use. The following procedures will be performed and the subject will exit the study:

- VFQ-25
- BCVA
- CS testing
- Cornea verticillata grading

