5. Ocular symptoms: Subjects will be queried at each visit “How are you feeling?” and treatment emergent AEs beginning at Visit 4 will be documented on the AE form. Additional symptoms reported after screening and before randomization will be documented on the medical history form. Adverse events will be recorded for every study visit (i.e., at 09:00, 11:00, and 16:00 hours) as needed.
6. Individuals returning at an Unscheduled Visit within 1 week to re-attempt IOP qualification are required to only re-measure IOP in both eyes.
7. Gonioscopy evaluation up to 3 months prior to randomization is acceptable.
8. Pachymetry within 1 week prior to screening is acceptable.
9. Entry visual field evaluation up to 3 months prior to randomization is acceptable. Visual field collection must meet the requirement for automated threshold visual field assessment (e.g., 30-2 or 24-2 Humphrey) and reliability.
10. Collect kit(s) dispensed during the Day 1 visit.

Observational Period

Study Procedures	OBS Visit 1 (Day 1) Visit when cornea verticillata is diagnosed	OBS Visits 2-4 Monthly Visit x3 (30 ± 5 days if Cornea Verticillata Persist)	OBS Visit 5 and up Bi-monthly Visits after 3 rd Monthly visit (60 ± 5 days if Cornea Verticillata Persist)	Final Visit if Resolution/ Stabilization of Cornea Verticillata ^{1,2} is confirmed
Discontinuation of IP	X			
Conmed Review	X	X	X	X
Symptoms/ Assessment of Ocular and General Health	X	X	X	X
VFQ-25	X			X
Best Corrected Visual Acuity	X	X	X	X
Contrast Sensitivity	X			X
Cornea Verticillata Grading	X	X	X	X

¹. Should have a grading score of zero OU or stabilization confirmed to exit the study.

². If cornea verticillata grading is zero at any visit, or stabilization of cornea verticillata is confirmed, the subject completes outlined procedures listed in Final Visit and exits the study.

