Randomized subjects will dose the assigned drug in both eyes QD in the evening (between 20:00 and 22:00 hours) beginning on Day 1 and up to and including the evening prior to the final visit at Visit 6 (Week 4). Procedures conducted at each of the Study Visits 4 to 6 will include safety and efficacy measurements, including IOP assessments. At Visits 4 to 6 (Weeks 1, 2, and 4, respectively), IOP will be assessed at 09:00, 11:00, and 16:00 hours. Following completion of the Visit 6 (Week 4) study visit procedures, subjects will exit the study. For subjects who discontinue early, every possible effort will be

made to assure there is a final visit that includes all examinations listed for Visit 6.0 (Week 4) and dilated ophthalmoscopy.

For subjects who show any evidence of cornea verticillata by slit lamp examination using the grading system for amiodarone keratopathy (Orlando 1984) during the 28-day treatment period, the assigned study drug will be discontinued, all exit visit procedures (Visit 6) will be completed and subject will be followed in an observational period starting as OBS Visit 1 (Day 1) in which subjects will undergo VFQ-25, BCVA testing, CS testing and cornea verticillata grading. All subjects with cornea verticillata will return for monthly surveillance visits (OBS Visit 2, 3 and 4) where they will undergo BCVA testing and cornea verticillata grading for 3 months. If cornea verticillata persists at the 3-month time point (OBS Visit 4), subjects will return every 2 months for BCVA testing and cornea verticillata grading until resolution or stabilization. Resolution is defined as grading of zero of the cornea verticillata grading and stabilization is defined as no worsening of the cornea verticillata grading for a minimum of one year from the commencement of dosing. Once resolution or stabilization is confirmed in both eyes, the subject will undergo VFQ-25, BCVA testing, CS testing and exit the study.

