14.3.6.9	Summary of Urinalysis and Urine Microscopic Categorical Values by Treatment Group and Visit	Safety Population
14.4.1	Subject Disposition Cornea Verticillata	Safety Population

14.4.2	Demographics and Baseline Characteristics by Treatment Group Cornea Verticillata	Safety Population
14.4.3.1	Number and Percentage of Subjects with Ocular Treatment-Emergent Adverse Events by Treatment Group, System Organ Class, and Preferred Term Cornea Verticillata	Safety Population
14.4.3.2	Number and Percentage of Subjects with Non-Ocular Treatment-Emergent Adverse Events by Treatment Group, System Organ Class, and Preferred Term Cornea Verticillata	Safety Population
14.4.4	Mean and Mean Change from Visit 1 in Visual Function Questionnaire (VFQ-25) Results by Treatment Group Cornea Verticillata	Safety Population
14.4.5.1	Mean, Mean Change from Baseline, and Mean Change from OBS Visit 1 in Study Eye Best Corrected Visual Acuity Results by Treatment Group Cornea Verticillata	Safety Population
14.4.5.2	Mean, Mean Change from Baseline, and Mean Change from OBS Visit 1 in Fellow Eye Best Corrected Visual Acuity Results by Treatment Group Cornea Verticillata	Safety Population
14.4.6.1	Summary of Contrast Sensitivity Testing in Study Eye by Treatment Group, and Visit Cornea Verticillata	Safety Population
14.4.6.2	Summary of Contrast Sensitivity Testing in Fellow Eye by Treatment Group, and Visit Cornea Verticillata	Safety Population
14.4.7.1	Mean and Mean Change from OBS Visit 1 in Study Eye Cornea Verticillata Grading by Treatment Group Cornea Verticillata	Safety Population
14.4.7.2	Mean and Mean Change from OBS Visit 1 in Fellow Eye Cornea Verticillata Grading by Treatment Group Cornea Verticillata	Safety Population
14.4.7.3	Time to Cornea Verticillata Resolution/Stabilization in Study Eye by Treatment Group and Overall Netarsudil-Treated Subjects Cornea Verticillata	Safety Population
14.4.7.4	Time to Cornea Verticillata Resolution/Stabilization in Fellow Eye by Treatment Group and Overall Netarsudil-Treated Subjects Cornea Verticillata	Safety Population

22. Listings

Listing Number	Title
16.1.7	Randomization Schedule
16.2.1.1	Subject Disposition
16.2.1.2	Subject Who Prematurely Discontinued
16.2.1.3	Subject Disposition for Screen Failure Subjects

16.2.2	Protocol Deviations
16.2.3.1	Analysis Populations Information
16.2.3.2	Inclusion Criteria Not Met/Exclusion Criteria Met for Screen Failures
16.2.4.1	Demographics and Baseline Characteristics

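### By-visit means of the cornea verticillata grade lose eyes that have cleared and exited, so later visits are selected toward persisting deposits

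*SAP*

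**What the plan says.** **Exit.** The observational-period schedule in Protocol Appendix 1 ties exit to the outcome. Footnote 1 reads "Should have a grading score of zero OU or stabilization confirmed to exit the study". Footnote 2 adds that on a grade of zero or confirmed stabilization "the subject completes outlined procedures listed in Final Visit and exits the study". SAP 3.1 agrees that exit is decided per subject: "Once resolution or stabilization is confirmed in both eyes, the subject will undergo VFQ-25, BCVA testing, CS testing and exit the study".

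**Return visits.** Protocol 7.4.2 makes further monthly visits conditional: "If cornea verticillata grading is higher than zero at this Month 1 Visit, the subject will return for a Second and/or Third Monthly Visit". Protocol 7.4.3 makes the bimonthly visits conditional on a grade above zero at OBS Visit 4. Protocol 3.1 and SAP 3.1, however, can be read as bringing every affected subject back for OBS Visits 2 to 4.

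**Summary.** SAP 16.4 states: "The scores and the score changes from Visit 1 will be summarized at eye level using continuous summary statistics by treatment group", and adds a split by whether the event is ongoing at the visit. The output in SAP Section 21 is Table 14.4.7.1, "Mean and Mean Change from OBS Visit 1 in Study Eye Cornea Verticillata Grading by Treatment Group", with Table 14.4.7.2 as its fellow-eye counterpart. The Protocol synopsis also plans grading summaries at the initial and follow-up visits.

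**Handling of cleared eyes.** SAP Section 16 has no rule for them. The missing-data methods in SAP 8.2 are written for the ITT and PP analyses.

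**Companion analysis.** SAP 16.5 plans eye-level Kaplan-Meier estimates of time to resolution or stabilization.

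**The concern.** Whether a subject is still observed depends on the variable being averaged. Someone attending a late visit is there because at least one eye still had deposits at the visit before. Subjects whose eyes have cleared contribute nothing more, and no rule keeps them in the denominator. A mean or mean change at a late visit then understates how far the affected eyes, taken together, have improved off drug.

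The ongoing split does not repair this. SAP 16.5 defines resolution as grade zero, and the documents give no other definition of when an event stops being ongoing. On the natural reading, one stratum holds only zeros and the other only grades above zero.

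This matters because Protocol 3.2 gives the resolution of verticillata in Japanese subjects, together with its effect on visual function, as the reason for long-term follow-up.

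**Working it through.** The plan states no figure on this point, so there is none to reproduce. The check has two parts: the direction, which needs no clearing rate, and an illustration of size, which does.

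**Direction.** Suppose a cleared eye stays clear, and the only exits so far are for grade zero in both eyes. Every eye that has left then has true grade 0, so the grades of all affected eyes sum to the same total as the grades of attending eyes. Hence

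mean among attenders = mean over all affected eyes ÷ share of affected eyes still attending.

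The share is at most 1, so the attender mean can only be equal or higher. Stabilization exits do not disturb this early on. They need a year from the start of dosing, and OBS Visit 1 falls no later than about Day 29, so none can occur before roughly 365 − 28 = 337 days after OBS Visit 1.

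**Inputs for the illustration**
- Visits at days 30, 60, 90 and 150 from OBS Visit 1 (Protocol 7.4.2 and 7.4.3).
- Return only if a grade is above zero (Protocol 7.4.2), and exit when both eyes grade zero (Appendix 1).
- The clearing-visit zero is counted at the visit where it is found.
- Assumed, not in the documents: grade 1 until clearing and 0 after; a constant clearing fraction p per 30 days (20%, 35% or 50%); no other losses.

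**Formulas.** The mean over all affected eyes at day d is S(d) = (1 − p)^(d/30). With d′ the previous visit:
- eyes clearing together, or one affected eye only: attender mean = S(d) ÷ S(d′);
- two eyes clearing independently: attender mean = S(d) ÷ [1 − (1 − S(d′))²].

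**Results at p = 35%**

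| Day | All affected eyes | Attenders, together | Attenders, independent |
|---|---|---|---|
| 30 | 0.650 | 0.650 | 0.650 |
| 60 | 0.423 | 0.650 | 0.481 |
| 90 | 0.275 | 0.650 | 0.412 |
| 150 | 0.116 | 0.423 | 0.245 |

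Worked case, day 90: S(90) = 0.65³ = 0.2746 and S(60) = 0.65² = 0.4225.
- Together: 0.2746 ÷ 0.4225 = 0.65.
- Independent: 0.2746 ÷ (1 − 0.5775²) = 0.2746 ÷ 0.6665 = 0.41.

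A simulation with between-eye correlation 0.8 gives 0.52, inside this range.

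**Other rates at day 90**
- p = 20%: 0.51 over all eyes, against 0.59 (independent) to 0.80 (together).
- p = 50%: 0.13 over all eyes, against 0.29 to 0.50.

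**Sensitivity to two unsettled points**
- *If every affected subject attends OBS Visits 2 to 4*, nobody has left by day 90 and there is no bias up to then. Attendance at day 150 still depends on the grade at day 90, so the day-150 row of the table is unchanged.
- *If the clearing visit is tabulated only in a Final Visit row*, the OBS rows hold only subjects who did not exit. At p = 35% and day 90 the mean is then 1.00 (together) or 1 ÷ (2 − 0.2746) = 0.58 (independent).

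**The case against.** A reader might infer that later visits show persisting deposits by construction, or that arms with different clearing rates would look alike. The documents do not support either reading.

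- **Exit is per subject, the summary per eye.** A cleared eye whose fellow persists stays in its table as zero.
- **The clearing grade is recorded.** Grading is part of the final-visit procedures in Protocol 7.4.4, so zeros do enter the data. With them counted at the visit where they are found, attender means can still fall, as the independent column shows. A completely flat profile from the start needs one affected eye (or both eyes clearing together) and the clearing visit filed only in a Final Visit row. That row would itself show the zeros, and SAP 8.5 may direct end-of-study data into such a row.
- **Clearing is analysed elsewhere.** In SAP 16.5 (Tables 14.4.7.3-4 and Figures 14.4.7.5-6) a cleared eye counts as an event, by treatment group.
- **Little rests on these tables.** They are descriptive and untested, and every grade is listed in Listing 16.3.7. At the 16.7% once-daily rate in Protocol 1.1, 52 subjects give about 52 × 0.167 = 8.7 cases per arm. Onset there ran over 2 to 13 weeks, against 28 days of dosing here.

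All of this limits the point without removing it. The Kaplan-Meier event pools resolution with stabilization, so an eye with unchanged deposits can count as an event. A Final Visit row shows the state at exit but not when clearing occurred, and no listed table gives the number of eyes cleared by visit. The ongoing split is redundant rather than harmful: its stratum counts cover attending eyes only.

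**Conclusion.** The point holds as a partial selection bias. Once subjects begin to exit for resolution, the grade means and mean changes planned in SAP 16.4 lean toward persisting deposits. The direction follows from the exit rule, provided cleared eyes stay clear and stabilization exits and other losses have not yet begun.

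The size is not established, because the documents give no clearing rate, grade mix or between-eye correlation. The example of 0.41 to 0.65 against 0.27 at day 90 rests on an assumed 35% clearing per 30 days and on the conditional-return reading of Protocol 7.4.2.

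The first follow-up visit is unaffected if the clearing zero is counted there. The equation of an ongoing event with a grade above zero is inferred, since the term is undefined and the status of a stabilized eye is not stated. This is a cheap improvement to descriptive safety tables; the primary endpoint is unaffected.

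**What to change.** Amend SAP 16.4 and Tables 14.4.7.1-2:

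1. At each scheduled OBS visit, report the number and percentage of eyes at each grade, including zero, with all eyes that ever had verticillata as the denominator.
2. Count eyes with documented resolution and exit as zero from then on, and footnote the assumption that they stay clear off drug.
3. Show stabilized exits and losses to follow-up as separate categories. Carrying a last grade forward after stabilization is optional.
4. Tabulate a clearing visit in its scheduled OBS row as well as in the Final Visit row.
5. Drop the ongoing split for the grade itself.

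Separately, Protocol 7.4.2 must be reconciled with Protocol 3.1 and SAP 3.1 on whether all affected subjects, or only those with a grade above zero, attend OBS Visits 2 to 4. That decides at which visit the selection begins.

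The table changes cost some SAP wording and reprogramming of two tables, with no new data. The one downside is the stay-clear assumption, which the footnote makes visible.
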